5. STUDY DESIGN

5.1 Study Design

This study is designed as a randomized controlled trial. Potential PCS participants will be referred to another member of the research team by [name]. Potential participants will then complete the informed consent process and pre screening checklist. Potential healthy participants will contact the research team directly and set up a time to complete the informed consent, pre screening process, and IPAQ. After being deemed eligible based on the screening criteria (screening checklist attached, section), PCS participants will be randomly assigned to either an AET or standard of care (SC) intervention (see section 7). Using minimization software, each intervention group will be balanced by age and sex. Healthy participants will serve as the control group (HC) and will receive no treatment. Once participants in the SC group have completed the study, the AET will be offered, although it will not be included in the data analysis. Following informed consent, PCS participants will be provided with Garmin VivoSmart HR unit to monitor aerobic activity outside of the study (accelerometer, heart rate monitor, and step counter capabilities). Participants will be required to wear the Garmin units as often as possible for the duration of the study. In place of the Garmin VivoSmart HR unit, participants in the HC group will complete the IPAQ to determine physical activity levels prior to participating in the study,.

All participants will compete a series of pre and post intervention assessments (see section 7.2) over the course of one week at Lakehead University. Following the pre intervention assessments,

participants in the AET group will complete an eight week aerobic and balance retraining program at the School of Kinesiology, Lakehead University (see section 7.2). Participants in the SC group will continue with his/her standard of care for eight weeks. Healthy participants will be instructed not to significantly change his/her lifestyle (diet, physical activity) for the duration of the study weeks. After eight weeks, all participants will complete the assessments once again.

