6.4 Procedures for Participant Enrolment /Allocation /Randomization

To achieve adequate enrolment, recruitment flyers will be placed at several locations and clinics around Thunder Bay. Once informed consent has been obtained, and the potential participant has been deemed eligible through the screening process, age and sex of the participant will be used to randomly assign the participant to an intervention group through a process called minimization. This process ensures group sizes are equal and eliminates potential bias that may be introduced which is important for clinical research of small sizes. The NOSM research assistant would then communicate the enrolment and group assignment to [name] who will administer the AET intervention. The SC intervention will continue under the supervision of the participant's healthcare provider. Participants will be assigned a code number by the research assistant to ensure confidentiality is maintained during the transfer of data or samples between locations.

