7.2 Description of Study Procedures, Assessments and Participant Activities

Once participants have been randomized into groups, participants will be scheduled to complete the pre intervention assessments at Lakehead University over a period of one week. These assessments will include a physical, cognitive, neuroimaging, biomarker, and driving behaviour assessment. These assessments will also be completed after the intervention in PCS participants, and after eight weeks in HC.

Physical and Cognitive Assessment:

Participants will complete the Immediate Post-Concussion Assessment and Cognitive Testing (ImPACT) at the School of Kinesiology, Sanders building, Lakehead University. The ImPACT will be used as a standard measure of cognitive abilities including: attention, working memory, processing speed, and reaction time. At a mutually agreed upon date and time, participants will meet a member of the research team at the Lakehead University Sanders Fieldhouse. Before beginning the assessments, a member of the research team will verbally restate the participant's rights and confirm that he/she is still willing to participate in the study.

Participants will then be set up at a computer station, where they will follow the on screen instructions for completing the ImPACT battery. Following completion of the ImPACT battery, participants will be asked to stand in a variety of static positions including: narrow based double leg stance, single leg stance, and tandem stance with one foot behind the other. Participants will perform each stance position with his/her eyes open and closed and on a firm and soft surface using the Balance Error Scoring System (BESS) protocol. Each stance will be performed over an AMTI force platform. This approach will be used to measure participant sway, centre of pressure displacement, and to count for the number of perturbation errors induced during the balance test³⁴. The session should last approximately one hour.

Biomarker Assessment:

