After completing baseline assessments, PCS participants assigned to the AET intervention will complete an eight week supervised AET program. The program will consist of three sessions per week, approximately 40-60 minutes each. Each session will be completed under the supervision of a trainer with the Canadian Society for Exercise Physiology (CSEP-CPT) certification. At mutually agreed upon dates and times, participants will meet a member of the research team at the Sanders building, room SB-1025. Before beginning the intervention, the member of the research team will verbally restate the participant's rights and confirm that he/she is still willing to participate in the study. Participants will then be outfitted with a Polar F2 heart rate monitor, in order monitor exercise intensity during the session. Exercise intensity for each session will be based on the participant's heart rate reserve (HRR). At the first session, the participants HRR will be calculated using the Karvonen formula; Target Exercise Heart Rate = $((220 - \text{Age} - \text{Resting Heart Rate}) \times \% \text{Intensity}) + \text{Resting Heart Rate}$. Once the participant's HRR has been calculated, the participant will begin the aerobic component of the session.

The aerobic component of the session will be performed on a cycle ergometer. Participants will begin with a five minute warmup at a self selected speed, which will be used to bring the participant's heart rate to the desired intensity. Intensity for each session will start at 20% of HRR, and increase linearly by 10% for the first four weeks; at week four, participants will be cycling at an intensity of 50%. Weeks five and six will be performed at 55% of HRR, week seven will be performed at 60% of HRR, and week eight will be performed at 65% of HRR. Duration will follow a similar pattern for weeks one to four, beginning at 20 minutes and increasing in five minutes/week increments. At week five, duration will be reduced to 25 minutes, and then increase to 30 minutes for weeks six to eight.

Following completion of the aerobic portion of the session, participants will rest for five minutes before beginning the balance component of the session. Participants will perform three balance exercises (in order) each session: narrow based double leg stance, single leg stance, and tandem stance. Difficulty of these exercises will be progressively increased by modifying the

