8. DATA MANAGEMENT

8.1 Data Collection

A trained member of the research team will obtain age (years), sex, height (cm), and weight (kg), as well as the pre screening form (see attached screening checklist, 16.3). This data will then be uploaded to the sync.com account and completed, if necessary, by [name].

[name] will administer the ImPACT and BESS. ImPACT results will be recorded and stored on the secured, password protected, ImPACT Applications, Inc. server. Data will be immediately coded by the researcher. BESS computer data will stored on a secure, password protected computer in [name] secure office (currently SB-1009).

[name] will oversee the collection of the saliva sample at the School of Kinesiology, Lakehead University. The research assistant will label the tube with the participant code and will transport it back to NOSM (unless already at NOSM), where it will be immediately processed.

Oddball and Flanker tasks will be overseen by [name] and [name]. All data will be collected and analyzed in [name] Laboratory at Lakehead University.

The driving simulation will be overseen by [name] at the Centre for Research on Safe Driving and recorded by the STISIM Drive[®] Model 400 driving simulator.

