12.3 Blinding Procedures

Participants will not be blinded to his/her group assignment. Participants placed into the SC group will be given the option of receiving the AET after completion of the study, although this will not be included in data analysis.

[name], [name], [name], and [name] will be blinded from group assignment for data analysis purposes.

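### Concussed participants are randomised before the baseline assessments, and the plan does not say the arm is withheld until those are finished, so baseline values may be taken with the arm known

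*Combined protocol and SAP*

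**What the plan says.** Section 5.1: once eligible, "PCS participants will be randomly assigned to either an AET or standard of care (SC) intervention"; the pre-intervention assessments are described after that step. Section 6.4 makes consent and eligibility the trigger and says that "age and sex of the participant will be used to randomly assign the participant to an intervention group", by minimisation. Section 7.2 is explicit about the order: "Once participants have been randomized into groups, participants will be scheduled to complete the pre intervention assessments", with the assessments spread over one week.

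On disclosure, Section 6.4 describes one step: "The NOSM research assistant would then communicate the enrolment and group assignment to" the person who will deliver AET (name removed). Section 12.3 says "Participants will not be blinded to his/her group assignment". It also says four team members are blinded for data analysis, and it is silent on blinding at the test sessions.

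On treatment timing, Section 7.2 says: "After completing baseline assessments, PCS participants assigned to the AET intervention will complete an eight week supervised AET program".

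The Section 7.1 schedule lists consent, screening, assessments A to D, intervention and post-assessment. It has no row for randomisation or for telling participants their arm.

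**The concern.** A baseline value is useful in a randomised comparison because it cannot depend on the arm. If a participant knows the arm when tested, that guarantee is lost for any measure that responds to effort or motivation. Someone who hoped for supervised exercise and was assigned to standard care might try less hard, or harder. The main analysis is the group-by-time interaction, so any arm-related shift at the pre-test that differs from the shift at the post-test becomes part of the estimated AET–SC difference in change.

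The second issue is loss. At the pre-assessment sessions staff are to "confirm that he/she is still willing to participate in the study", and by then the participant has been allocated. A person who leaves at that point counts as randomised but lacks some or all of the outcome baseline. The missing-data rule in Section 10 excludes them from each affected change analysis. If leaving is related to the arm, the groups compared are no longer the groups randomised.

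The healthy controls are not randomised, so both issues concern AET versus SC only.

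**Working it through.** **1. Order of events.** Sections 5.1, 6.4 and 7.2 agree: consent, screening, allocation, pre-assessments, then AET. Section 7.1 contains nothing that alters this. The interval between allocation and the first assessment is not given.

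**2. Is there a safeguard?** A statement that the arm is withheld until assessment D would answer the bias point, and none of the available sections contains one. Starting AET after baseline controls exposure to treatment, not knowledge of the arm. Blinding four people for data analysis does not blind the participant.

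**3. Is early allocation needed?** Section 6.4 minimises on age and sex, which do not depend on the baseline tests. AET starts after baseline. The documents give no reason for allocating earlier.

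**4. Which Section 11.2 measures are exposed?** The section names ERP, balance, BDNF and reaction time.
- Reaction time: Section 10 spells this out for the driving simulator. It is plainly effort-dependent.
- ERP: the Section 2 hypotheses and Section 10 make averaged amplitude and latency the oddball and flanker outcome. These may vary with attention, so an effect is possible.
- Balance: possible.
- Salivary BDNF: little exposed.
- ImPACT is effort-dependent but is not in Section 11.2; Section 10 gives it a separate pre/post comparison.

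**5. How a shift enters the estimate.** Let b be the AET-minus-SC shift at pre-test caused by knowing the arm, and c the same shift at post-test, both in SD units.
- Present order: bias in the difference in change = c − b.
- Allocation after baseline: b = 0, so bias = c.

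If c = b, the present order happens to cancel. If c = 0, the whole of b is bias and the new order removes it.

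**6. Illustration with assumed inputs.** The documents give no b, c, SD or pre–post correlation ρ. Assume b = 0.3, c = p × b, no true effect, 20 per arm (Section 5.2) and a two-sided 5% t-test on change scores with 38 df. The SD of change is √(2(1 − ρ)) and the non-centrality is |bias| / √(2(1 − ρ)) × √(20/2). For p = 0 in the present order this is 0.3/1 × 3.162 = 0.95 at ρ = 0.5, and 0.3/0.632 × 3.162 = 1.50 at ρ = 0.8.

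| Fraction p persisting to post-test | False-positive rate, present order (ρ = 0.5 / 0.8) | After reordering |
|---|---|---|
| 0 | 15% / 31% | 5% / 5% |
| 0.5 | 7.5% / 11% | 7.5% / 11% |
| 1 | 5% / 5% | 15% / 31% |

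With b = 0.2 the largest values are 9.5% / 16%. The two columns mirror each other, so the table shows the mechanism and not a net gain. Under this model, reordering lowers the error only if less than half the shift persists.

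**7. Loss during baseline.** One person is 1/20 = 5% of an arm. The documents predict no number of such losses. Age, sex and date of injury would still be on file (Sections 8.1 and 16.4).

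**The case against.** The strongest objection is that the decisive fact is missing. No section says when a participant learns the arm, and the one communication described goes to the person running AET. The removed consent pages might settle it. What the documents establish is an order of steps and silence about disclosure; arm-aware baselines are an inference. This stands, and it is why the point says may.

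The illustration also shows no net reduction in error. If most of a shift persists to the post-test, the present order gives the lower false-positive rate. That is correct, so the percentages carry no weight in the conclusion. Such cancellation would, however, be accidental and could not be verified, so it is no reason to keep the order.

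The attrition argument is thin in size: 5% of an arm is true of any lost participant, and no baseline-week loss is forecast. Section 11.1 asks for 12 per group against 20 planned, which leaves room for power, though not against selective loss.

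Three stronger readings are tempting, and the documents support none of them:
- **The testers know the arm.** Section 8.1 says a team member "will administer the ImPACT and BESS", but the name is removed, so nobody can tell whether that person is the one told the assignment in Section 6.4.
- **Oddball and flanker button responses are contaminated endpoints of the main analysis.** No section clearly places them in Section 11.2.
- **The false-positive rate is inflated to some stated figure.** Every input to such a figure would be assumed.

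**Conclusion.** The concern holds as a weakness in the stated order, not as a demonstrated bias. Three facts carry it: allocation precedes baseline in three sections, participants are unblinded, and no available text withholds the arm. The change is also cheap. Size and direction are unknown. Reordering secures two things: pre values that cannot depend on the arm, and an outcome baseline for everyone randomised. It does not touch open-label influence at the post-test.

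A reader might infer that the randomisation is compromised or the trial invalid. The documents do not support that: the order does not affect how the arm is generated, and AET still begins after baseline. The change should be made, with medium confidence. If the arm is already withheld in practice, a sentence saying so closes the bias point and leaves only the pre-baseline loss.

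**What to change.** Amend Sections 5.1, 6.4, 7.1 and 7.2 so that the order is consent, screening, pre-assessments A to D, QMinim allocation, then disclosure of the arm. Add a randomisation row to the Section 7.1 schedule after assessment D. Do not randomise anyone who leaves during baseline.

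If allocation must stay early, state that the arm is withheld from participants and testers until assessment D is complete. That addresses the bias but not the pre-baseline loss.

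Visits, tests and staff are unchanged. The amendment needs Research Ethics Board approval (Section 14.2). It also leaves less lead time for booking AET sessions three times a week: one week of pre-assessment, eight of AET and one of post-assessment already fill the 10 weeks in Section 5.4 (1 + 8 + 1 = 10). That is manageable, but not free.

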To date, the majority of randomized controlled trials (RCTs) have used rest and psychological approaches to alleviate persistent concussion symptoms and have focused on providing individuals with recovery-related information, reassurance, or education. Most of these studies have found no benefit or reported inconclusive findings¹⁰. Of the research that has focused on treatment, AET¹¹ has shown to be promising for overall symptom reduction. The conclusions of these studies, however, are limited by the lack of control groups, biased samples, and the inclusion of TBIs of all severities. In addition, many of the interventions were delivered prior to the period when symptoms are typically considered persistent. Controlled studies are needed to test the specific effects of treatment on the persistent symptoms in a post-concussion syndrome sample lasting greater than one month post-concussion. The intervention we plan to test is AET in a controlled/stepwise exercise training program using RCT methodology. Recent evidence indicates that an active rehabilitation program may be useful for individuals with persistent concussion symptoms¹² and that exercise can also be effective at improving mood¹³.

Studies have also shown that levels of brain-derived neurotrophic factor (BDNF) are significantly increased as a result of aerobic exercise in healthy individuals. In particular, preliminary data from our group¹⁴ demonstrated an increase in salivary BDNF levels in a healthy control group following 4 weeks of AET (the same protocol we are proposing). BDNF is a secreted protein that has been shown to play a central role for neural health and brain plasticity^{15,16}. BDNF has been demonstrated to be a useful biomarker of brain injury post-concussion¹⁷ with animal research showing significantly reduced levels of BDNF several hours or days after a concussion¹⁸. Notably, aerobic fitness and BDNF share a relationship that is predictive of memory performance in healthy individuals¹⁹⁻²¹. Also, it is known that executive function and circulating BDNF both decline with age, however, changes in serum BDNF

predicts improvements in cognitive outcomes in response to aerobic exercise in older individuals²².

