2. It is anticipated that AET will result in increased efficiency of neural processing during cognitive tasks in post measures compared to SC and with less difference than compared to HC compared to pre- intervention comparisons. Cognitive efficiency will be measured by the amplitude and latency of two event related electrical potentials associated with attention and conflict monitoring processing.
3. It is anticipated that concussed participants receiving the AET will exhibit improved balance. This will be measured using the force platform centre of pressure area, displacement, and velocity measures while completing the various static stance positions using the BESS protocol.
4. It is anticipated that concussed participants receiving the AET will exhibit increased improvements in salivary BDNF levels, indicative of an improvement in concussion symptoms. Salivary BDNF will be quantified using the BDNF ELISA assay and changes in pre- vs. post-intervention concentrations will be assessed. Additionally, we hypothesize that lower levels of BDNF upon entry to the study will indicate more pronounced concussive symptoms. This relationship will be determined by correlating the pre-intervention BDNF concentration to measures of the post intervention assessments.

5. It is anticipated that concussed participants receiving the AET will exhibit improved reaction times compared to the SC group during dual tasking scenarios to avoid crashing in dangerous traffic situations.

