5.4 Length of Participation

Participation in this study will last 10 weeks, depending on scheduling of the pre and post intervention assessments. Pre intervention assessments will be conducted at Lakehead University before beginning intervention. The AET intervention will occur three times per week for eight weeks. Each session will last approximately one hour. The SC intervention will be ongoing throughout the eight weeks. The HC group will not complete an intervention. Final assessments will be completed after any intervention has concluded.

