Brain-derived neurotrophic factor (BDNF) will be assessed using a morning saliva sample. Participants will be asked to refrain from brushing his/her teeth, smoking, and consuming food or drink within two hours of the sample collection. Participants will also be asked to avoid alcohol consumption 12 hours prior to sampling. At a mutually agreed upon date and time, the participant will meet a member of the research team at the Sanders building, Lakehead University. Before beginning saliva collection, the member of the research team will verbally restate the participant's rights and confirm that he/she is still willing to participate in the study. Saliva will then be collected from participants in room SB-1025 (biohazard containment level 1) via the passive drool method into a tube, which will then be put on ice and transported to [name] lab for processing. Processed saliva samples will be stored until samples have been collected from all participants. If the sample is collected immediately prior to the physical and cognitive assessments, participants will be provided with light refreshments after saliva has been collected.

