duration, surface, and whether the participant's eyes are open or closed. For weeks one and two participants will perform the exercises with his/her eyes open; participants will perform each exercise for 15 seconds on a firm surface in week one, and on a low density foam block in week two. In weeks three and four, participants will perform the exercises with his/her eyes closed; exercises in week three will be performed on a firm surface, while week four will be performed on a low density foam block. Duration will be increased to twenty seconds per exercise for weeks three and four. Weeks four to eight will follow the same eyes open/closed and surface progression as weeks one to four; eyes open for weeks five and six, eyes closed for weeks seven and eight. Exercises will be performed on a firm surface in weeks five and seven, and on a low density foam block in weeks six and eight. Participants will perform each exercise for 35 seconds in weeks five and six, and 40 seconds in weeks seven and eight. Following the completion of the aerobic and balance components of the session, participants will complete a cool down consisting of a series of static stretches. Each session will conclude after the completion of the cooldown.

After completion of 24 sessions (eight weeks x three-one hour sessions per week), participants will repeat the procedures for the previously described baseline assessments. Similarly, HC and SC participants will complete the baseline assessments again after eight weeks.

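### Saliva sampling rules leave recent exercise uncontrolled, so a short-term effect of the last AET session, if there is one, would be mixed into the group-by-time BDNF comparison

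*Combined protocol and SAP*

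**What the plan says.** **Sampling rules.** Section 7.2 (Biomarker Assessment) fixes the time of day: "Brain-derived neurotrophic factor (BDNF) will be assessed using a morning saliva sample". It then lists what to avoid: "Participants will be asked to refrain from brushing his/her teeth, smoking, and consuming food or drink within two hours of the sample collection" and "Participants will also be asked to avoid alcohol consumption 12 hours prior to sampling". Neither this section nor section 9 (Specimen Management) mentions exercise.

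**Timing of the post sample.** Section 7.2 (Aerobic and Balance Retraining Program) says: "After completion of 24 sessions (eight weeks x three-one hour sessions per week), participants will repeat the procedures for the previously described baseline assessments". Section 5.4 says: "Final assessments will be completed after any intervention has concluded". Both give an order of events, and neither gives an interval. Section 5.1 spreads the assessments over one week, and section 7.2 leaves the saliva appointment to mutual agreement.

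**Exercise and BDNF.** Section 1 says that BDNF levels "are significantly increased as a result of aerobic exercise in healthy individuals". The salivary example it gives is a rise in healthy controls after four weeks of the same programme.

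**Use of the result.** Hypothesis 4 in section 2 expects AET participants to "exhibit increased improvements in salivary BDNF levels, indicative of an improvement in concussion symptoms". Section 11.2 tests BDNF by the interaction of group (AET, SC, HC) and time (pre, post) in a mixed ANOVA. The model has no term for time since exercise.

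**The concern.** The protocol controls several nuisance exposures before the sample but omits the one that its own rationale links to the analyte. The omission does not fall evenly on the arms. The baseline sample precedes any AET session. The post sample follows a block of three supervised sessions a week, and week eight has the highest prescribed intensity of the programme (65% of heart rate reserve). SC and HC have no scheduled exercise at either time point.

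A transient effect of a recent session, if it exists, would therefore tend to appear in one arm at one visit. That is the pattern the group-by-time interaction is built to detect. Randomisation does not remove it, because it arises after allocation. Blinding the analysts does not remove it either, because it is in the sample itself.

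What is at stake is the interpretation of the secondary objective, BDNF as a marker of response to AET. A rise could reflect recovery, a training effect or simply a recent session, and the plan records nothing designed to tell these apart. Goal 3, which correlates BDNF change with improvement in symptoms and balance, would also carry extra noise if the interval since exercise varied between participants.

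**Working it through.** The plan states no figure on this point, so there is none to reproduce. The check is mainly a comparison of the text.

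**Step 1: is exercise before sampling restricted anywhere?** No.
- Section 7.2 restricts teeth-brushing, smoking, food and drink (two hours) and alcohol (12 hours).
- Section 5.1 tells HC participants to keep their usual lifestyle. That is a general instruction to one group, not a rule about sampling.
- Section 12.1 permits all relevant concomitant care and interventions.

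**Step 2: how short can the gap be between the last session and the sample?**
- Sections 5.4 and 7.2 require only that the programme has finished.
- Section 5.4 gives 10 weeks of participation, which fits one pre week + eight intervention weeks + one post week = 10.
- Within the post week the sample may fall on any morning. The morning after session 24 is compatible with the text. A sample on the same day is not barred.

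**Step 3: could the interval be recovered from planned data?** Only in part.
- Section 13 says that intervention visits are documented, but the data abstraction form in section 16.4 shows no field for time of last session or time of saliva collection.
- Section 5.1 gives Garmin units to PCS participants, to be worn as often as possible. HC participants complete the IPAQ instead, before the study.
- No planned BDNF analysis uses any of these data.

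**Step 4: illustration of sensitivity.** The documents give no SD and no acute effect for salivary BDNF, so the shift d below is an assumption. It is the average shift over the whole AET group, in SDs of pre-to-post change, with no other effect in any group.

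Inputs: n = 20 per group (section 5.2); alpha 0.05, two-sided (section 11.1).

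- AET versus SC, t test on change: df = 2 × 20 − 2 = 38, critical value 2.024, non-centrality = d × √(20/2).
- Three-group interaction, equivalent to a one-way ANOVA on change: df = 2 and 57, critical value 3.159, non-centrality = 20 × d² × 2/3.

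| Assumed d | t non-centrality | AET vs SC significant | F non-centrality | Interaction significant |
|---|---|---|---|---|
| 0 | 0 | 5% | 0 | 5% |
| 0.2 | 0.632 | 9.5% | 0.533 | 9.0% |
| 0.3 | 0.949 | 15.2% | 1.200 | 14.5% |
| 0.5 | 1.581 | 33.8% | 3.333 | 33.7% |

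Because d is an average, an acute effect of 1.0 SD in half of the AET group gives d = 0.5 × 1.0 = 0.5 (ignoring the added spread). The pairwise test and the planned interaction test give nearly the same picture. The table shows how sensitive the comparison would be to a shift. It is no evidence that a shift occurs.

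**The case against.** **No acute mechanism is documented.** Section 1 describes BDNF rising as a result of aerobic exercise, and its salivary example is a change over four weeks of training. That is the effect under test, not a contaminant. No section describes a rise after a single session or how long one would last. This objection stands, and it limits the point to an uncontrolled exposure with a possible effect.

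**Same-day sampling is unlikely.** A morning collection after two hours without food or drink fits poorly with a 40–60 minute session earlier that morning. Sampling the next morning or later is the more natural reading. This stands as a matter of likelihood, but the text does not exclude same-day sampling and sets no gap for any other day.

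**Other groups exercise too.** A reader might infer that a short-term rise could occur only in AET and only at the post visit. The documents do not support that: SC and HC participants may exercise before either sample, and AET participants may exercise before baseline. What remains is narrower: only AET has scheduled sessions near the post sample, so imbalance between arms is the expected direction.

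**Part of the information exists.** Visit records and Garmin data might allow time since exercise to be reconstructed for much of the PCS sample. That helps, but wear is voluntary in extent, HC has no units, and no analysis is planned.

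**BDNF is secondary.** It is one of four outcome families in section 11.2. This bears on priority, not on whether the gap exists.

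**Conclusion.** The point holds in a limited form. The sampling rules omit exercise, no minimum interval follows the last AET session, and only AET has scheduled exercise near the post sample. If recent exercise affects salivary BDNF in the short term, the effect would be unbalanced between arms and could not be separated from the change that hypothesis 4 treats as symptom improvement.

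The size is unknown. The rates of about 9.5% to 34% rest wholly on assumed average shifts of 0.2 to 0.5 SD of change, 20 analysed per group and no other effect. They should not be read as an estimate of the trial's error rate. A reader might also conclude that a positive BDNF result would be an artefact of recent exercise. The documents do not support that, because they neither describe an acute salivary rise nor require sampling soon after a session. This is a worthwhile standardisation of a secondary outcome and does not threaten the trial as a whole.

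**What to change.** 1. Add one sentence to the saliva instructions in section 7.2: a single exercise-free interval before each sample, identical for all three groups and both time points. The investigators should set its length and justify it, since the documents offer no basis for a particular value. It can be met by choosing the saliva appointment, without altering the exercise programme.
2. Add fields to the data abstraction form (section 16.4) for the date and time of last exercise and of saliva collection, at both visits and in all groups.
3. Add to section 11.2 a pre-specified sensitivity analysis of the BDNF comparison by time since last exercise, using Garmin data where available to check the reported times in PCS participants.

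The cost is one sentence, a few recorded fields and a small scheduling constraint in the assessment weeks. No change to sample size or to the main model is needed.
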